## **9. Research methods**

### **9.1 Study design**

To answer the objectives, this study will use an Moderna vaccination targeting SARS-CoV-2-exposed case-cohort design and a myocarditis cohort study design (Figure 1).

The case-cohort design will be used to assess risk factors other than Moderna vaccination targeting SARS-CoV-2 for the development of myocarditis and pericarditis in recipients of the Moderna vaccine targeting SARS-CoV-2, to understand which characteristics increase or decrease the risk for the development of myocarditis and pericarditis after vaccination (i.e., t0). This may contribute to risk assessment and identification of individuals who do not have an increased risk on myocarditis or pericarditis.

[figure not shown]
The cohort design will be used to describe prognostic factors for a (severe) clinical course in patients with myocarditis or pericarditis regardless of vaccination status. As most myocarditis and pericarditis cases are mild in disease severity, it is clinically relevant to identify the individuals who are at increased risk for severe clinical outcomes as early as possible, in order to provide appropriate care in a timely manner. These severe outcomes are acute coronary syndrome, acute myocardial infarction, heart failure, atrial fibrillation/flutter, ventricular arrhythmias/cardiac arrest, pulmonary embolism or deep venous thrombosis, stroke outcomes, peripheral arterial embolism, hospital readmission, ICU admission or death. Therefore, information available at the onset of myocarditis or pericarditis (i.e., t1) could be used to predict the clinical course including long-term outcomes (i.e., t2).

The cohort design will also be used to address both secondary study objectives. Within the cohort of myocarditis/pericarditis cases, clinical course and risk profiles will be compared between patients with myocarditis/pericarditis recorded after vaccination targeting SARS-CoV-2 and patients with myocarditis/pericarditis unrelated to vaccine administration. Moreover, risk factors for severe myocarditis/pericarditis will be investigated within this cohort.

Recipients of Moderna vaccination targeting SARS-CoV-2 and cases of myocarditis and pericarditis will be identified between January 2021 (date of the earliest approval of Moderna vaccines targeting SARS-CoV-2 in Europe) and the end of the study period (defined as most recent data availability at the time of the End of Data collection).

### Figure 1 Overview of the Study Designs

[figure not shown]
Figure 1. Schematic of study designs: patient selection

- a. In the case-cohort design all myocarditis/pericarditis cases are selected among individuals who received Moderna vaccination targeting SARS-CoV-2. The controls will be sampled from the exposed cohort, sampled to align with the distribution of cases based on month and year of documented vaccination receipt. For the cohort design, all myocarditis and pericarditis cases from the available databases will be selected.

**Figure 2 Case-cohort design**

[figure not shown]

- a. Up to a 45-day gap in medical or pharmacy enrollment allowed
- b. Risk factors may include demographic characteristics, lifestyle factors, medical history, and vaccination characteristics
- c. Earliest of: outcome of interest (myocarditis), death, end of the study period, leaving network, lost to follow-up

*\*If 2 doses within 90 days: index on first dose. If more than 90 days since last dose: re-indexing.*

*\*\* A <45 day gap for changes in insurance is not expected for European Union (EU) Data Access Providers (DAPs).*

**Figure 3 Cohort design**

\* A <45 day gap for changes in insurance is not expected for EU DAPs.

### 9.1.1 Moderna vaccination targeting SARS-CoV-2-exposed case-cohort

To assess risk factors for development of post-vaccine myocarditis and pericarditis, a cohort of Moderna vaccination targeting SARS-CoV-2 recipients will be defined in each participating database. This set will be used for the first primary objective.

For the case-cohort design, individuals with at least one dose of Moderna vaccination targeting SARS-CoV-2 will be used to define a cohort of Moderna vaccination recipients. Cases are those individuals who develop myocarditis or pericarditis any time during the follow-up after Moderna vaccination targeting SARS-CoV-2. The controls will be sampled from the exposed cohort, such that they align with the distribution of cases based on the month and year of documented Moderna vaccination receipt.

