**Data sources:**

This study is planned as analysis of routinely collected health data in five secondary automated electronic data sources in four countries (Denmark, Norway, Spain, and the United Kingdom [UK]). The data access providers (DAPs) are selected based on availability of the required routinely collected data, including information on vaccine brand and frequency of data updates, in cooperation with the established VAC4EU association. As feasible, linkage to medical records is planned for case confirmation and if applicable, collection of data on risk factors and outcomes not available in structured data. Local laws and regulation will apply for case validation and data collection.

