### 9.2.2 Inclusion criteria

For the Moderna vaccination targeting SARS-CoV-2-exposed case-cohort design, a cohort will first be defined including individuals of all ages with (1) at least one dose of Moderna vaccination targeting SARS-CoV-2 administered during the study period, (2) at least one year of enrolment in the applicable database prior to the index vaccine dose to allow for ascertainment of baseline covariables and potential risk factors, and (3) no myocarditis or pericarditis events within 6 months prior to Moderna vaccination receipt. Myocarditis and pericarditis cases are defined when adjudication criteria according to the Brighton Collaboration Case Definition for possible, probable or definite myocarditis or pericarditis is fulfilled. Cases and controls are defined as mentioned in [Section 9.1.1](#).

In the cohort design, all cases following vaccination, and only a sample of cases not following vaccination will undergo adjudication. In the analyses, individuals will be included if they: (1) have been adjudicated and meet the adjudication criteria according to the Brighton Collaboration Case Definition for possible, probable or definite myocarditis or pericarditis, and (2) have at least one year of enrolment in the applicable database prior to the index myocarditis or pericarditis event to allow for ascertainment of baseline covariates and potential risk factors.

For both the case-cohort as the cohort design, individuals with administrative codes for myocarditis or pericarditis will be identified in each data source. Following this initial screening, selected cases will be confirmed based on review of clinical data (based on criteria according to the Brighton Collaboration). The selection will include all cases of myocarditis and pericarditis following Moderna vaccination targeting SARS-CoV-2, as well as an age- and sex- matched sub-sample of other cases.

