### **9.2.3 Exclusion criteria**

Individuals not meeting criteria outlined in [Section 9.2.2](#) are excluded from the Moderna vaccination targeting SARS-CoV-2-exposed case-cohort and myocarditis/pericarditis cohort analyses, respectively. For the cohort design an additional exclusion criterium is applied: Persons with no record of a Moderna vaccine targeting SARS-CoV-2 but record of another vaccine for SARS-CoV-2 within 30 days prior to index date of myocarditis or pericarditis event will be excluded. Individuals who have evidence of myocarditis or pericarditis in structured data (e.g., ICD-10 codes) where review of clinical data is not performed due to sampling, or is incompatible with adjudication criteria according to the Brighton Collaboration Case Definition for myocarditis or pericarditis will be described but will not be included as cases in primary analyses. In the Moderna vaccination targeting SARS-CoV-2-exposed case-cohort design, non-confirmed myocarditis/pericarditis cases will be censored at the onset of the false positive myocarditis/pericarditis diagnosis.

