**Table 2 Summary of the data sources by country**

Country	Denmark	Norway	Spain	Spain	UK
Data access partner	Aarhus University	University of Oslo	IDIAP	FISABIO	DSRU
Type of data	Record linkage	Record linkage	Record linkage & GP	Record linkage & GP	GP medical record and linked datasets
Data source name	Danish registries	Norwegian registries	SIDIAP	VID	CPRD
Size of data in 2019	5.8 M	5.4 M	5.8 M	5M	16 M
Diagnosis coding	ICD-10	ICD-10CM/ICPC	ICD-10CM	ICD-9CM/ICD-10/ICD-10CM	MEDCODE IDs/ICD-10 (for some linked datasets)
Hosp. discharge diagnoses	Yes	Yes	Yes	Yes	Yes
Intensive care unit (ICU) admission	Yes	Yes	No	Yes	Yes
Extracorporeal membrane oxygenation (ECMO) use	Maybe	Maybe	No	Yes	Yes
Date of death	Yes	Yes	Yes	Yes	Yes
Emergency unit visit diagnoses	Yes	Yes	Yes	Yes	Yes
Outpatient specialist visit diagnoses	Yes, hospital outpatient specialist clinics	Yes	Yes, referrals to specialists	Yes	Yes
Primary care diagnoses	No	Yes	Yes	Yes	Yes
COVID-testing	Routine testing only during early pandemic	Routine testing only during early pandemic	Routine testing only during early pandemic	Routine testing only during early pandemic	Routine testing only during early pandemic
Medicines dispensing outp.(pharmacy)	Yes	Yes	Yes	Yes	No
Medicines inpatient	Some	Yes, but not accurate	No	Yes	No
Medicines prescribing	No	No	Yes	Yes	Yes
COVID-19 Vaccine brand	Yes	Yes	Yes	Yes	Yes

In addition to the structured data available in these databases, medical record data will be reviewed to confirm myocarditis and pericarditis case characteristics.

In the SAP the exact variables that are required to answer all research questions will be defined, resulting in a data instance, which is a document that contains information about which data point can be found in which data source for every DAP and in which CDM table this will be stored.

The data instance is created in collaboration with the DAP. Extracting the data is done by the DAPs, following the data instance, and results in the CDM tables that contain all the data points that are required for the study.

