and might make some (subgroup) analyses challenging regarding achieving adequately powered statistical analyses. Data availability may also limit our ability to address primary and secondary study objectives related to the identification of lifestyle factors as risk factors for the development of myocarditis/pericarditis. While the merits of investigating lifestyle factors as potential risk factors may be questioned when the data availability cannot be assured, we believe it is central to the research question to consider and rule out potential confounders whenever possible. Namely, we want to be able to determine the risk of myocarditis or pericarditis following vaccinations targeting SARS-CoV-2 over and above other common factors (e.g., age, smoking status). To this end, we will investigate as many lifestyle factors as feasible across all DAPs. Where not feasible (i.e., certain DAPs are missing a given lifestyle factor), analyses will include a smaller subset of variables and/or will only be done for those DAPs that have the requisite data available.

The sampling of cases (i.e., myocarditis or pericarditis not following vaccination) to be validated could pose a limitation in the characterization of the clinical course of cases not following vaccination. As most myocarditis and pericarditis cases following vaccination are expected to occur in young adults, age-matched non-vaccine related myocarditis/pericarditis cases will also mainly comprise of young adults. This may lead to an underrepresentation of non-vaccination related cases in older individuals in the cohort analysis. However, the sensitivity analysis including all cases, regardless of being validated or not, will provide information regarding the clinical course of non-vaccine related cases in possible underrepresented age groups.

There are a few other potential validity issues in this study. Selection bias is not expected to pose a threat to validity, as the routinely collected data are sufficiently representative of the background population. That is, the registries have full population coverage in Denmark and Norway, while the regional databases in Spain are representative with respect to background rates and demographic distributions of the underlying populations. Similarly, the CPRD is broadly representative of the UK population (see [Annex 3](#)).

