- The GAIA Pharmaceutical module stores data on all outpatient pharmaceutical prescriptions and dispensings, including both primary care and outpatient hospital departments, using the Anatomical Therapeutic Chemical (ATC) classification system and the National Pharmaceutical Catalogue, which allow the identification of the exact content of each dispensing. GAIA does not include in-hospital medication or medication administered in the Accident and Emergency Department (AED). GAIA provides detailed information on prescriptions issued by physicians, such as the duration of treatment and dosage.
- The Hospital Medical Record (ORION) provides comprehensive information covering all areas of specialised care, from admission, outpatient consultations, hospitalisation, emergencies, diagnostic services (e.g., laboratory tests, imaging, microbiology, pathology), pharmacy, surgical block including day surgery, critical care, prevention and safety, social work, at home hospitalisation, and day hospitalisation. ORION is currently in the process of being integrated for the whole region, with several databases already fully integrated and available for all hospitals, including the Minimum Basic Data Set at Hospital Discharge (MBDS) and the AED clinical record.
- The MBDS is a synopsis of clinical and administrative information on all hospital admissions and major ambulatory surgery in the Valencia health system hospitals, including public-private partnership hospitals (approximately 450,000 admissions per year in the region). The MBDS includes admission and discharge dates, age, sex, geographic area and zone of residence, main diagnosis at discharge, up to 30 secondary diagnoses (comorbidities or complications), clinical procedures performed during the hospital episode, and the diagnosis-related group(s) assigned at discharge. The MBDS used the ICD-

9-CM system for coding through December 2015 and ICD-10-ES afterward. The MBDS was extended in 2015 to include the “present on admission” diagnosis marker and information on tumour morphology.

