proportion of the CPRD panel practices (>80%), the GPs have agreed to permit CPRD to link at patient level to the Hospital Episode Statistics (HES) data. CPRD is listed under the ENCePP resources database, access will be provided by the DSRU. The CPRD was not yet characterised in the ADVANCE project, where the UK THIN and RCGP databases were used, but has been largely used in vaccine studies. The HES database contains details of all admissions to National Health System (NHS) hospitals in England; approximately 60% of GP practices in the CPRD are linked to the HES database. Not all patients in the CPRD have linked data (e.g. if they live outside England or if their GP has not agreed that their data should be used in this way). As with standard CPRD patients, HES data are limited to research-standard patients. CPRD records are linked to the HES using a combination of the patient's NHS number, gender and date of birth. The Drug Safety Research Unit (DSRU) is the leading UK centre for pharmacovigilance and pharmacoepidemiology which has led and coordinated many large studies across the UK. The Unit has ample experience of monitoring the post-authorisation safety of vaccines, notably active surveillance on the H1N1 swine flu vaccine and an active surveillance study and six enhanced passive surveillance studies on the children's seasonal influenza vaccine. The DSRU works with the UK's National Institute for Health Research (NIHR) Clinical Research Network, which facilitates research in the National Health Service (NHS) and provides access to a large network of research-ready health care professionals, including GPs. The DSRU also has experience of study designs based on patient reported outcomes.

Signature Page for VV-CLIN-016832 v1.0

2nd Approval	PPD [Redacted] PPD [Redacted] 26-Jan-2024 11:39:43 GMT+0000
--------------	---

2nd Approval	PPD [Redacted] PPD [Redacted] 26-Jan-2024 16:04:33 GMT+0000
--------------	---

Signature Page for VV-CLIN-016832 v1.0

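### Case-cohort cases need reviewable clinical records but controls do not, so uneven record access within a database would bias the odds ratio of any candidate factor that tracks access

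*Protocol*

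**What the plan says.** **Cases.** Section 9.2.2: "Myocarditis and pericarditis cases are defined when adjudication criteria according to the Brighton Collaboration Case Definition" at the possible, probable or definite level are fulfilled. Section 9.4 adds that, beyond the structured data, "medical record data will be reviewed to confirm myocarditis and pericarditis case characteristics". The abstract makes this conditional: "As feasible, linkage to medical records is planned for case confirmation", subject to local law. Under section 9.2.3, coded cases that are incompatible with the criteria, or not reviewed because of sampling, "will be described but will not be included as cases in primary analyses". In the case-cohort, non-confirmed cases are censored at what that section calls a false positive diagnosis. Section 9.7.5 foresees a Level 4 class of insufficient information and admits it only to an optional expanded sensitivity analysis.

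**Controls.** Section 9.1.1: "The controls will be sampled from the exposed cohort, such that they align with the distribution of cases", the alignment being on month and year of vaccination. Entry to the exposed cohort (9.2.2) needs a dose in the study period, a year of prior enrolment and no recent event. It does not ask whether the person's records could be reviewed.

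**Record access.** Annex 3 says of the Valencia hospital medical record: "ORION is currently in the process of being integrated for the whole region". Of the UK source it says: "Not all patients in the CPRD have linked data (e.g. if they live outside England", or if the GP has not agreed.

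**Bias statement.** Section 9.9: "Selection bias is not expected to pose a threat to validity", because the data represent the background population.

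**The concern.** Controls should represent the people who would have been counted as cases had they developed the disease. Here the case side passes through a filter (records obtainable and sufficient) that the control side does not. If the filter is unrelated to every candidate factor, only precision is lost. If it is related to one, that factor acquires an odds ratio of its own making, and a true null can appear harmful or protective.

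Primary objective 1 rests on these odds ratios. Healthcare utilisation (9.3.3) and geography (named in the abstract) are candidate factors that could plausibly follow record access. The representativeness argument in 9.9 concerns who is in the database, not which coded cases survive validation. Section 9.9 does note that validation may reduce case numbers, but treats this only as a loss of power.

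**Working it through.** **1. The plan's own size figure.** Recipients in section 9.5, Table 3: 675,345 + 1,646,900 + 1,386,090 + 3,107,305 + 28,536 = 6,844,176. At 0.4 to 4.0 per 100,000 this gives 27.4 to 273.8 cases, which reproduces the stated 27-274. The later per-database ranges also reproduce: 5 x 20-80 = 100-400 myocarditis cases and 5 x 50-140 = 250-700 pericarditis cases. The protocol gives no figure for record access.

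**2. Effect of the filter.** Let r1 and r0 be the probabilities that a coded case's records can be reviewed, with and without a factor, and p the factor's prevalence in the exposed cohort.
- Odds of the factor among confirmed cases: p x risk1 x r1 / [(1-p) x risk0 x r0].
- Odds among controls (rare outcome): p / (1-p).
- Expected OR = (risk1/risk0) x (r1/r0) = true OR x r1/r0.

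**3. Numbers.** Assumptions, not in the protocol: true OR 1, p = 50%, and the r1 and r0 values below. At 90% v 60%, the factor's share among confirmed cases is 0.45 / (0.45 + 0.30) = 60%, against 50% in controls, so OR = (0.60/0.40) / (0.50/0.50) = 1.50.

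Chance of a nominally significant result (two-sided 5%, four controls per case as in 9.5), at the ends of the expected case ranges per database:

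| Access r1 v r0 | Expected OR | 20 cases | 50 cases | 80 cases | 140 cases |
|---|---|---|---|---|---|
| 90% v 90% | 1.00 | 5% | 5% | 5% | 5% |
| 90% v 75% | 1.20 | 5.5% | 8.2% | 10.8% | 15.8% |
| 90% v 60% | 1.50 | 12.0% | 24.0% | 35.8% | 56.4% |

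If access is lower with the factor, the OR is the reciprocal: 0.75/0.90 = 0.83 and 0.60/0.90 = 0.67.

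**4. Check by simulation.** Conditional logistic regression in vaccination strata, 80 cases, 320 controls, true OR 1, 150 repeats:
- Even access at 90%: OR about 0.97, significant in 3%.
- 90% v 60%, controls from the whole exposed cohort: OR about 1.52, significant in 36%.
- 90% v 60%, controls restricted to people with reviewable records: OR about 1.03, significant in 3%.

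The 1,000 control draws in section 9.5 do not help. They reduce sampling noise, and this is a bias common to every draw.

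**5. Where it could arise.** Models are fitted and reported per database (9.7.2), so only variation within a database matters. FISABIO holds 3,107,305 / 6,844,176 = 45% of recipients, and its hospital record, which holds laboratory and imaging data, is not yet integrated region-wide. The UK source holds 28,536 / 6,844,176 = 0.4%. That is 0.1 to 1.1 myocarditis cases at the literature incidence, although the preliminary estimate is 20-80 per database.

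**The case against.** The strongest reply is that uneven access to reviewable charts is not demonstrated. Annex 3 says that in Valencia the discharge dataset and the emergency record already cover all hospitals, and that the ambulatory record has 96% coverage. UK linkage to HES is linkage to a structured admissions file, not chart access, and Annex 3 offers validation against specialist letters with no HES condition. Section 9.3.3 names country of residence, which is essentially constant within a database, rather than sub-national geography. Nothing in Annex 3 ties access to age group. Section 9.7.5 already lists Level 1-4 and all-coded-case analyses. Handling of unobtainable records may also be set out in the SAP or the adjudication plan.

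Most of this stands, and it limits the point. A reader might infer that a person without linked records can never become a case. The protocol does not support that: the questionnaire adapts the Brighton definition to the elements available (8.2), possible cases qualify, and other records may suffice. A reader might also infer that Annex 3 proves the bias. It makes unevenness plausible and no more.

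What the reply does not remove is the asymmetry. Insufficient information takes a person out of the primary case set, and nothing comparable acts on controls. The control frame and the 9.9 statement are fixed in the protocol whatever the SAP adds. The 9.7.5 analyses are optional and subject to feasibility. The all-coded-case version also brings false positives back in, and section 9.9 invokes it only for age groups underrepresented among cases not related to vaccination.

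**Conclusion.** The point holds in conditional form. If access to reviewable records differs within a database according to a candidate factor, the primary case-cohort OR for that factor is multiplied by the ratio of access probabilities, and no planned mandatory analysis would show it. The size rests wholly on assumed access rates: nil if access is even, a factor of 1.20 at 90% v 75%, and 1.50 at 90% v 60%. Differences between databases do not contribute. It would be too much to say that any particular risk factor will be distorted, since the protocol gives no access rate. Two statements need correcting in any case: 9.2.3 does not separate a record that could not be obtained from one reviewed and refuted, and 9.9 gives representativeness as the reason for expecting no selection bias. The change is worth making because it is cheap and the affected ORs answer a primary objective.

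**What to change.** 1. In each database where record access depends on something known for everyone at the index dose (linked practice, integrated hospital area), apply that condition to both the cases and the control sampling frame in the primary analysis. Keep the unrestricted frame as a sensitivity analysis.
2. Where access cannot be known for non-cases, make the Level 1-4 and all-coded-case analyses in 9.7.5 mandatory for the case-cohort. Tabulate reviewed against unreviewable coded cases by candidate factor.
3. In 9.2.3, separate records that are unobtainable or insufficient from records reviewed and refuted, and state how each is handled.
4. Amend 9.9 so that representativeness is not offered as the reason this selection is absent, and name it as a limitation.

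Cost: one flag per database where it can be defined, one table and two text changes. The control pool should remain ample at four controls per case. Some generalisability is lost. It should not be assumed that no cases are lost: an imperfect flag may drop a few that were confirmed through other records, such as specialist letters.
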